Utilizing Stanisic et.al findings, our protocol will only include patients with a pre-operative hematoma volume of **115cc** or greater. Similar to this group, we will perform monthly interval CT scans until the total hematoma volume is measured to be less than **80cc**³⁷ our working definition of resolution. At this point, we will determine that the patient has met criteria for **resolution** of the cSDH and would not require further imaging. If the patient demonstrates a neurological change or increased volume, an earlier CT scan will be performed, regardless of volume size.

Conclusion

The current literature and our own preliminary data have demonstrated that there is local elevation of pro-inflammatory chemokines and pro-angiogenic factors within the subdural hematoma cavity of chronic subdural hematomas that are not found systemically. CXCL8 (IL-8) demonstrates both pro-inflammatory and pro-angiogenic properties. Curcumin has shown to directly inhibit the production and activity of CXCL8 (IL-8) *in vitro* and *in vivo*, as well as down regulating the activity of VEGF and bFGF. These combined effects make CC an important anti-inflammatory and anti-angiogenic molecule that has the potential to reduce the recurrence rate of chronic subdural hematomas. We expect that CC will prevent/reduce persistent hemorrhage within the subdural hematoma cavity, by blocking IL-8-induced disruption of the blood vessels. Specifically, CC is expected to preserve blood vessel leakage and accumulation of blood in SDH cavity, by blocking destructive effect of IL-8 on the vascular endothelial tight junctions.

3. Study Design

This is a *double-blinded, randomized placebo-controlled pilot study*. The patients, neurosurgeons, nurses and clinical coordinators will be blinded except for the research pharmacists who will keep a key linking a code # on a bottle handed to the clinical coordinator and the patient's MRN #. The pill bottles handed to the clinical coordinator will be identical for placebo and CC.

Study Type: Interventional

Study Design: Randomized Treatment assignment

Intervention Model: Parallel Assignment

Masking: Double Blind (Subject, Investigators, coordinators, nurses)

Primary Purpose: Treatment

Intervention:

1) Curcumin (turmeric extract), over the counter supplement (1 capsule/three times a day).

Producer Company: Oregon Wild Harvest

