3.2.2 Exclusion criteria

- Age < 18 years old
- Bilateral subdural hematomas
- Subdural volume $< 115\text{cc}$
- Acute subdural hematoma
- Patient does not undergo surgical evacuation
- Other evidence of intracranial injury (i.e. epidural hematoma, intraparenchymal hemorrhage, skull fractures, subarachnoid hemorrhage, hydrocephalus)
- Patient's family not available for consent and requires emergent surgical evacuation
- Previous intracranial surgery
- Recent head trauma (< 1 week)

Title: Clinical Action of Curcumin/Turmeric In chronic Subdural hematoma recurrence (CACTIS)

- Use of anti-coagulation (i.e. Coumadin, Heparin, Apixaban, and Rivaroxaban) or anti-platelets (Plavix) drugs, with the exception of Aspirin
- Known coagulopathy disorders
- Positive urine or serum pregnancy test in pre-menopausal female subjects, without a documented history of surgical sterilization; or currently breastfeeding

1.1.1.□.1. Since the nuclear group in an older population, the pregnancy test will be made in exceptional cases.

- Allergy to curcumin or turmeric.
- Allergy to black pepper
- Markwalder Grading Scale

1.1.1.□.1. Score: 3-4

- Baseline dementia (for more than 6 months).
 - Adult who cognitively impaired for more than 6 months will be excluded from the study, since this impairment might be due to other reasons than cSDH, such as dementia or cognitive impairment.

4. Number of Subjects

This is a single center pilot study. A total of 48 subjects will be recruited in this study.

24 patients will receive placebo pills, and 24 will receive Curcumin (CC) pills. Patients will be first stratified according to their pre-surgery hematoma volume. Randomization will be performed within each hematoma volume group (12 subjects per hematoma volume group) to ensure equal distribution between placebo and CC groups.

Study Timelines

- Duration of an individual subject's participation in taking CC or placebo will be for up to a maximum of 60 days, with follow-up at 6 months and 18 months
- Clinical follow-up with CT scans will be up to 6 months, depending on if residual total hematoma volume < 80cc
- Enrollment of subjects will continue for 2 years.
- Complete data analysis will be performed within 2 years.

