Patients who have symptomatic unilateral chronic subdural hematomas, with no acute component and do not meet the exclusion criteria, will be evaluated. At the time of consent for evacuation of the subdural hematoma, patients will also be consented for this trial by the research team. They will be instructed that they will be randomized to either the placebo group or the curcumin group. They will take one capsule three times a day for a maximum of 60 days. They will undergo standard post-operative care in regard to imaging and clinical follow-up.

Evaluation:

1. Patient evaluated by neurosurgery resident

Title: Clinical Action of Curcumin/Turmeric In chronic Subdural hematoma recurrence (CACTIS)

2. Patient or POA consented by Neurosurgery resident for cSDH evacuation in the operating room.
3. Evaluated by research team for inclusion into trial within 48 hours of presentation to the Neurosurgery service
4. Consent patient or POA for trial participation

Interventions:

1. *Intra-operatively*, patient has samples sent to lab
 - a. At least 10 cc of subdural hematoma fluid will be collected during the initial and recurrence operative, along with 5 cc blood from an existing IV
 - b. The SDH fluid and blood samples will be sent to [name] lab and used in the experimental setup within 10-15 days of collection and in addition analyzed for inflammatory cytokines/chemokines.
2. *Presurgical randomization by stratified hematoma volume.* Presurgical hematoma volume randomization is important because recurrence of cSDH has been shown to be related to presurgical hematoma volume by Stanisic et al.³⁷ The hematoma volume and other CT characteristics are recorded as shown in **Table 1** below.
 - a. Hematoma volume will be recorded and stratified into two groups according to hematoma volume: >140 ml and \leq 140 ml. The process of stratification and subsequent randomization will be done by the IDS pharmacist who will conceal the randomization results from all study team members until after the results of the study have been analyzed.
 - b. After the first patient is consented, we will record his or her hematoma cavity volume. All subjects will be assigned to a treatment group to receive either curcumin-containing or non-curcumin-containing capsules.

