 - c. For the next patient, we will first determine the hematoma cavity volume group; this patient's Tx assignment (CC or placebo) will be alternate to the immediately preceding patient. This process is repeated until all of the patients are enrolled.
3. The patients will start medication **within 24 hours after surgery**, or as soon as they are able to take oral medication
 - a. 1 capsule three times a day (with breakfast, lunch, and dinner) for a maximum of 60 days or until resolution of subdural hematoma
 - b. Resolution will be defined as residual total hematoma cavity volume $<$ 80cc
 - i. If the post-subdural drain removal scan demonstrates a residual total hematoma volume $<$ 80cc, the patient will not be included in the study sample; although, the patient may receive more than one dose of CC by the time of the CT scan.

- CT Imaging:
 - Pre-operative CT SOC scan-- If the hematoma volume is $<$ 115 cc, the patient will not be included in the study
 - Post-operative day one CT SOC scan
 - Post subdural drain removal SOC scan--If the residual total hematoma cavity volume is $<$ 80cc, the patient will be removed from study, as the curcumin has not had time to influence the patient's reabsorption.
 - During the SOC 1 week follow-up appointment, the attending will decide on the need for a repeat CT scan in 4 weeks based on the patient's **post-subdural drain removal SOC scan**. The considerations for re-evacuation include: lack of resolution of the initial clot, an obvious increase in size of the clot, persistent headache, onset of seizures, or onset of new deficit or headache. These criteria will be used in all subsequent considerations for surgical re-evacuation.

Title: Clinical Action of Curcumin/Turmeric In chronic Subdural hematoma recurrence (CACTIS)

- If the residual total hematoma volume is $\geq 80\text{cc}$, the patient will receive an additional CT scan (SOC) for an appointment one month following the previous appointment (Approximately post-operative day 37)
- If there is a decline in neurological exam or other clinical concern, the neurosurgeon may perform an earlier CT scan
- This will continue on a monthly basis for 6 months, or until residual total hematoma cavity volume is $< 80\text{cc}$
 - **Resolution** will be defined as residual total hematoma cavity volume $< 80\text{cc}$
 - Patients with resolution of their hemorrhage will no longer require follow-up visits. Their pills will be returned and discarded.

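### The stated allocation rule is strict alternation, not randomization: one known assignment gives away the sequence, and read literally the hematoma-volume stratification has no effect

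*Combined protocol and SAP*

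**What the plan says.** Section 3 (Study Design) labels the trial: "Study Design: Randomized Treatment assignment". Section 4 (Number of Subjects) plans 48 patients, 24 per arm, and states: "Randomization will be performed within each hematoma volume group (12 subjects per hematoma volume group) to ensure equal distribution between placebo and CC groups". Section 9 (Study Procedures, Interventions, item 2.a) sets the strata at above 140 ml and at or below 140 ml. It adds: "The process of stratification and subsequent randomization will be done by the IDS pharmacist", with the result concealed from the study team until the analysis is done.

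Items 2.b and 2.c then say how this is carried out. For the start: "After the first patient is consented, we will record his or her hematoma cavity volume". That patient is to be assigned to an arm, but no random mechanism is given. For every later patient the volume group is determined first, and then the assignment "Tx assignment (CC or placebo) will be alternate to the immediately preceding patient". The item ends: "This process is repeated until all of the patients are enrolled". It does not say whether the preceding patient is the last one enrolled or the last one in the same volume group.

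**The concern.** Alternation is a fixed rule, so the trial as written is not randomized. Two things are at stake.

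**Predictability.** Section c (Data Management/Confidentiality) puts the enrolment number in each subject identifier. If alternation is overall and every numbered patient is allocated in order, odd and even identifiers are the two arms. Staff can then see from the outset which patients share an arm, and only the label is hidden. Coordinators and investigators obtain consent (section m), and they know the enrolment order and the CT volume. Someone who learns or guesses one assignment can decide whether to approach the next patient knowing the arm. The attending decides re-evacuation on judgement-based considerations, and one clinician sees every trial patient (Section 9, Clinic Follow-up). The rate of surgical intervention is a secondary endpoint (5.1.4). Predictable allocation therefore threatens both who enters the trial and how an outcome arises.

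**Stratification.** Item 2 justifies stratifying on the ground that recurrence is related to pre-surgical volume. If the preceding patient is simply the last one enrolled, the volume group is recorded but never used, and the promised balance is left to chance.

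**Working it through.** **Inputs from the protocol.** N = 48, 24 per arm (Section 4); two volume strata (Section 9, item 2.a); the alternation rule (item 2.c). **Assumption.** The documents do not give the share of patients above 140 ml, so p = 0.5 and p = 0.7 are shown (0.3 gives the same results as 0.7).

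**1. The plan's own totals.** Alternation over 48 patients gives exactly 24 and 24, as Section 4 states. The totals therefore cannot show whether allocation was random.

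**2. Number of possible sequences.**
- Overall alternation: 2, one for each starting arm.
- Alternation within stratum: 2 × 2 = 4.
- Random 24/24 list: C(48,24) = 3.22 × 10^13.
- Random 12/12 list in each of two strata of 24: C(24,12)² = 7.31 × 10^12.

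**3. What one disclosure reveals.** Under alternation, patients j and k share an arm if k − j is even and are in opposite arms if it is odd.
- Overall: one known assignment gives 47 of the 47 others.
- Within stratum: it gives all others in that stratum, or 23 of 23 if the stratum holds 24.
- Random permuted blocks of 2 and 4 within stratum, for comparison: guess the opposite arm for the patients immediately before and after, and toss a coin for the rest. In simulation this predicts about 51% of the other assignments in the stratum, close to chance.

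**4. Balance within a volume group under overall alternation.** Let X_C and X_P be the numbers above 140 ml in the two arms, each Binomial(24, p) and independent. For D = X_C − X_P, SD(D) = √(2 × 24 × p(1 − p)).
- p = 0.5: √12 = 3.46
- p = 0.7: √10.08 = 3.17

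Since the arms total 24 each, the difference in the other stratum is −D. Exact tail probabilities:

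| Share above 140 ml | P(difference ≥ 4) | P(difference ≥ 6) | P(difference ≥ 8) |
|---|---|---|---|
| 0.5 | 0.31 | 0.11 | 0.03 |
| 0.7 | 0.27 | 0.08 | 0.02 |

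Simulation agrees. An unstratified random 24/24 list gives the same 31% and 27%, so under this reading the volume step has no effect on balance.

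**5. If stratum sizes are fixed.** The figure of 12 per volume group reaches 48 only as 12 per arm per stratum (2 × 2 × 12), that is, 24 per stratum. Suppose exactly 24 of the 48 are above 140 ml and arrive in random order. Then X_C is hypergeometric with variance 24 × ½ × ½ × 24/47 = 3.06. With D = 2X_C − 24, SD(D) = 2 × 1.75 = 3.50, P(difference ≥ 4) = 0.39 and P(difference ≥ 6) = 0.15. Fixing the stratum sizes does not rescue the literal rule.

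**6. The other schemes.** Alternation within stratum keeps the difference to at most 1. Permuted blocks of 2 and 4 within stratum keep it to at most 2; blocks of 4 and 6 keep it to at most 3.

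**The case against.** The strongest reply is that the wording is loose and the design sound. Sections 3 and 4 and item 2.a all speak of randomization, and a pharmacist carries it out and conceals it. Item 2.c determines the volume group before assigning treatment, which makes sense only if the alternation is within group. Stratification then works, with tighter balance than permuted blocks, and the imbalance figures above do not apply. Those figures measure the loss of stratification, not the harm of alternation, and no bias in any endpoint has been quantified.

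Much of this is fair. The within-group reading is plausible, and the imbalance figures hold for the literal reading only. Coded bottles and matching capsules lower the chance of a first disclosure, and the predictability argument depends on one. Consent is tied to surgical consent, so there is little room to re-time a patient, though declining to enrol one remains possible. Fisher's exact test can also be justified by binomial sampling, and here it serves secondary outcomes. Patients below 80 cc on the post-drain scan are removed after allocation, so no list can guarantee balance among those analysed, and any replacement would take the number allocated above 48.

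None of this supplies a random sequence. Under either reading the arms follow a fixed pattern, and a pharmacist can conceal a list but not a published rule. Pilot status can excuse low power, but not non-random assignment in a trial described to patients as randomized. If block randomization was intended, item 2.c contradicts Section 4 and item 2.a and needs the same edit.

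**Conclusion.** The concern holds and must be fixed. The protocol promises stratified randomization, but its only operational rule is deterministic. With overall alternation there are 2 possible sequences, one disclosure reveals all 47 other assignments, and volume balance is no better than without stratification: SD about 3.2 to 3.5 and a 27% to 39% chance of a difference of 4 or more, depending on the assumed stratum split. With alternation within stratum, balance is good (at most 1), but there are only 4 sequences and one disclosure reveals the whole stratum. The loss of randomization does not depend on which reading is right. Predictability requires one assignment to become known or guessed, which blinding makes less likely but does not rule out. The size of any resulting bias cannot be calculated from the documents.

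**What to change.** Delete the alternation rule in Section 9, item 2.c, and rewrite items 2.b and 2.c. State that the statistician generates by computer, before the first patient, a separate permuted-block list for the above-140 ml and the at-or-below-140 ml groups. Randomly varying blocks of 2 and 4 would serve. IDS alone holds the lists and assigns the next entry in the patient's stratum after consent and recording of volume. Block sizes should be kept out of the protocol. The exact block sizes are secondary; what matters is an unpredictable sequence in each stratum.

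In the same edit, bring Section 3, Section 4 and item 2.a into line with the new text, and clarify that 12 per volume group means 12 per arm in each stratum, if that is intended.

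The cost is one protocol paragraph and a list generated once. A biostatistician is already a co-investigator (Data Analysis, Statistical analysis). No extra patients, visits or staff are needed, and the sample size stays at 48.
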